**7.5.8 Visit 8 – 5 Weeks Post Lead Placement**

The subject will return approximately 5 weeks after the initial lead placement. [REDACTED]

**7.5.9 Visit 9 – 6 Weeks Post Lead Placement**

The subject will return approximately 6 weeks after the initial lead placement. [REDACTED]

**7.5.10 Visit 10 – 7 Weeks Post Lead Placement**

The subject will return approximately 7 weeks after the initial lead placement. [REDACTED]

**7.5.11 Visit 11 – EOT**

**8 Weeks Post Lead Placement: lead removal and end of treatment (EOT)**

The subject will return approximately 8 weeks after the initial lead placement. [REDACTED]

**Visit 12 – conducted 1 week after EOT**

Subjects will return to the clinic 1 week after the end of treatment (EOT). [REDACTED]

**7.5.13 Visit 13 – Follow-up visit**

**conducted 1 month (4 weeks) after EOT**

Subjects will return to the clinic 4 weeks after EOT. [REDACTED]

**7.5.14 Visit 14 – Telephone Follow-up  
conducted 2 months (8 weeks) after EOT**

[REDACTED]

**7.5.15 Visit 15 – Telephone Follow-up  
conducted 3 months after EOT**

[REDACTED]

**7.5.16 Visit 16 – Follow-up visit  
conducted 4 months after EOT**

[REDACTED]

**7.5.17 Visit 17 – Telephone Follow-up  
conducted 5 months after EOT**

[REDACTED]

**7.5.18 Visit 18 – Telephone Follow-up  
conducted 6 months after EOT**

[REDACTED]

[REDACTED]

[REDACTED]

**7.5.19 Visit 19 – Telephone Follow-up  
conducted 7 months after EOT**

[REDACTED]

**7.5.20 Visit 20 – Telephone Follow-up  
conducted 8 months after EOT**

[REDACTED]

**7.5.21 Visit 21 – Telephone Follow-up  
conducted 9 months after EOT**

[REDACTED]

**7.5.22 Visit 22 – Follow-up visit  
conducted 10 months after EOT**

### 7.5.23 Unscheduled visits/Lead Replacements

Subjects may need to return to the clinic for an unscheduled visit if they experience an adverse event that requires further evaluation [REDACTED] experience a technical issue with the system, or require a bandage change or lead replacement. [REDACTED]

### 7.5.24 Study Visit Windows

The acceptable windows for each visit are listed in Table 3.

**Table 3 Study Visit Windows**

| Visit Number | Visit Name          | Window     |
|--------------|---------------------|------------|
| n/a          | Consent             | [REDACTED] |
| 1            | Baseline            | [REDACTED] |
| 2            | Lead Placement      | [REDACTED] |
| 3            | Telephone Follow-up | [REDACTED] |
| 4            | 1 week Stimulation  | [REDACTED] |
| 5            | 2 week Stimulation  | [REDACTED] |
| 6            | 3 week Stimulation  | [REDACTED] |
| 7            | 4 week Stimulation  | [REDACTED] |
| 8            | 5 week Stimulation  | [REDACTED] |
| 9            | 6 week Stimulation  | [REDACTED] |

|    |                          |  |  |
|----|--------------------------|--|--|
| 10 | 7 week Stimulation       |  |  |
| 11 | 8 week Stimulation / EOT |  |  |
| 12 | 1 week post EOT          |  |  |
| 13 | 1 month post EOT         |  |  |
| 14 | 2 months post EOT call   |  |  |
| 15 | 3 months post EOT call   |  |  |
| 16 | 4 months post EOT        |  |  |
| 17 | 5 months post EOT call   |  |  |
| 18 | 6 months post EOT call   |  |  |
| 19 | 7 months post EOT call   |  |  |
| 20 | 8 months post EOT call   |  |  |
| 21 | 9 months post EOT call   |  |  |
| 22 | 10 months post EOT       |  |  |

### 7.6 Early termination

[REDACTED]

### 7.7 Subject compensation

Individuals [REDACTED]

[REDACTED] will receive [REDACTED] compensation for full participation in all study visits to cover expenses while taking part in this study. Compensation will be disbursed as individuals complete certain milestones within the study. [REDACTED]

The disbursement schedule will be as follows:

- [REDACTED] after the completion of Visit 1
- [REDACTED] after the completion of Visit 2 Screening
- [REDACTED] after the completion of Visit 2 Testing
- [REDACTED] after the completion of each Visit 4-13, Visit 16, and Visit 22
- [REDACTED] after the completion of each Visit 14, 15, and 17-21 phone calls

If a subject volunteers to participate in an additional study visit #2 (returns for another session of stimulation testing) the subject will receive [REDACTED] compensation at the completion of that visit. If a Group #2 subject requires lead replacement after Visit 4, the subject will receive [REDACTED] compensation at the completion of the replacement.

If a subject participates in an unscheduled visit (other than an additional visit #2), they will receive [REDACTED] compensation for completion of that unscheduled visit.

[REDACTED]

[REDACTED]

## 8.0 Data management

### 8.1 Subject screening and identification logs

A subject screening log will be completed at each investigational site for all subjects who were considered for the study. Subject identification log will be completed for subjects enrolled in the study.

### 8.2 Data collection

For this study, an Electronic Data Capture (EDC) system which utilizes electronic CRFs (eCRFs) will be used. A 21 CFR Part 11 compliant system will be selected for use which enables entry of study data into an Electronic Data Capture system by each participating clinical site. The EDC system will be validated prior to being available for data entry at the sites and will include appropriate electronic security measures such as controlled password protected access, storage and back-up on the data on a secure HTTP (SSL) server, and appropriate data entry logic and validation checks.

[figure not shown]
Paper source documents, where applicable, will be completed and maintained in a fashion that is consistent with accepted Good Clinical Practices. If necessary, corrections to the source documentation will be made by using a single line strikeout with the initials and date of the person making the correction. The corrections will be made so as not to obscure the original data. Correction fluid or correction tape may not be used. Where specified, the Principal Investigator must sign and date the source documentation and questionnaires.

All paper study documentation will be stored in a locked storage facility (either a locked office or a locked cabinet).

After subject randomization, all surveys will be administered by a study team member who will not know the randomization assignment of each subject and thus will be designated as a Blinded Evaluator.

[figure not shown]
### 8.3 Subject numbering

Eligible consecutive subjects will be given a unique alpha - numerical study ID number.

### 8.4 Confidentiality of data

Every effort will be made to protect subject confidentiality. Subject names and personal identifiers will not appear in any publications resulting from this work

[REDACTED]

[REDACTED]

**9.0 Outcome analysis**

All primary and secondary endpoint data will be analyzed and reported. This study is a randomized placebo-controlled [REDACTED] study. The goal of the study is to gather data regarding the safety and effectiveness of percutaneous PNS for the treatment of post-amputation pain. Descriptive statistics will be used to summarize baseline subject characteristics within each treatment group. Baseline characteristics include both demographic variables as well as variables such as baseline pain intensity, time elapsed from amputation, medications affecting pain used at baseline, prosthesis fit, and the baseline BDI-II score. These characteristics will be examined via a covariate analysis.

[REDACTED]

**9.1 Primary clinical efficacy endpoint analysis**

[REDACTED]

The effectiveness of percutaneous Peripheral Nerve Stimulation (PNS) for the treatment of post-amputation pain will be assessed in the present study. The goal of the proposed [REDACTED] study is to determine if the investigational treatment produces pain relief that is clinically meaningful and greater than the placebo effect. To distinguish between the effect of the investigational treatment and the placebo effect, qualifying individuals will be randomized (1:1) to either Group #1 (Treatment) or Group #2 (Control). The groups will be identical except for whether active stimulation (Group #1) or sham stimulation (Group #2) is delivered during the first 4 weeks of the home trial. Both groups are expected to experience a similar placebo effect from the study procedures and use of the devices. In Group #1, subjects will experience both the placebo effect and the investigational treatment effect. During the sham stimulation phase in Group #2, subjects will experience only the placebo effect. Thus, if there is a difference between the mean improvements during sham stimulation and active stimulation, it can be attributed to the investigational treatment effects.

The null hypothesis ( $H_0$ ) is that the investigational treatment (Group #1, active simulation) is equal to the control (Group #2, sham stimulation) in providing pain relief. The alternative hypothesis ( $H_1$ ) is that Group #1 has a proportion of successes that is not equal to the proportion of successes of Group #2.

1.  $H_0$ : proportion of successes of Group #1 = proportion of successes of Group #2
2.  $H_1$ : proportion of successes of Group #1  $\neq$  proportion of successes of Group #2

If the proportion of successes of the investigational treatment is statistically significantly greater ( $p < 0.05$ ) than the proportion of successes of the control during the first 4 weeks of the home trial and the alternative hypothesis is accepted at the 0.05 level of significance, it will indicate that the investigational treatment is clinically significant and different than the placebo effect.

Pain relief will be evaluated using the average pain intensity. All regions of post-amputation pain (RLP or PLP or both) that have intensities  $\geq 4$  on average during the baseline period and receive treatment with an investigational device will be used to assess the primary efficacy endpoint. All amputees will record two daily post-amputation pain scores (one daily score for RLP and one daily score for PLP) for each amputated leg in the 7-day diaries using BPI-SF Question #5. For each individual, the region(s) of post-amputation pain with a 7-day average  $\geq 4$  during baseline in a leg that receives blinded treatment from an investigational device(s) will qualify to be used in the determination of clinically-meaningful success for that subject throughout the study. Each amputee must have  $\geq 50\%$  reduction in all areas of qualifying RLP and PLP to be considered a success in the primary effectiveness endpoint analysis.

The primary endpoint of the study compares the proportion of subjects in Group #1 relative to that in Group #2 that achieve  $\geq 50\%$  reduction in all areas of qualifying post-amputation pain from baseline to the first 4 weeks of the home trial, examining the statistical superiority of proportion of clinical successes of Group #1 over the proportion of successes of Group #2. The post-amputation pain intensity scores will be determined for each subject by taking the mean of the daily average pain intensity (BPI-SF Question #5) reported in the 7-day diary at baseline compared to the mean score for the same region(s) of pain reported over the first 4 weeks of the home trial (*i.e.*, the average of all diary scores during this period). For each leg with leads, the average pain scores will only include the days when all leads are in place (e.g., if leads are placed in second leg during week 2 of home trial, then only the data from weeks 2-4 will be used). Data will be collected as described in the Schedule of Procedures (Appendix A).

**9.1.1 Baseline characteristics and changes in usage of medication affecting pain will be analyzed to determine how strong their relationships are with changes in pain intensity between baseline and EOT**

The following variables: sex, age, baseline pain intensity, time elapsed from amputation, medications affecting pain used at baseline, prosthesis fit, baseline BDI-II score, and percent changes in usage of medication affecting pain between baseline and EOT (i.e., PRN medication usage) will be examined via a covariate analysis to determine their influence on the primary outcome.

**9.1.2 A power analysis of the 2-tailed, 2-sample Mann-Whitney test was conducted for the primary efficacy endpoint to determine the sample size for > 90% power and a 5% significance level**

A power analysis of the 2-tailed, 2-sample Mann-Whitney test was conducted with data from the previous feasibility study and data published in other studies. The proportion of successes expected for Group #1 was estimated from the previous feasibility study in which stimulation produced comfortable sensations (paresthesia) in the region of greatest pain. The proportion of successes expected for Group #2 was estimated from published studies in which sham (placebo) treatments were given to amputees with post-amputation pain. The null hypothesis that the proportion of successes of Group #1 is equal to the proportion of successes of Group #2 was tested.

[REDACTED]

[REDACTED]

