**7.5.2.7 Bilateral Amputees**

*Bilateral amputees may also receive up to 2 SPRINT Systems for their second leg if it meets the same criteria*

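### Success requires every qualifying region to respond, so the baseline number of regions is prognostic by construction, but the visible primary comparison and the 9.1.1 covariate list do not use it

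*Combined protocol and SAP*

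**What the plan says.** **Success rule.** Section 9.1 takes every region with a baseline diary mean of at least 4, in a leg that gets blinded treatment, and requires at least a 50% "reduction in all areas of qualifying RLP and PLP to be considered a success in the primary effectiveness endpoint analysis". Each subject contributes one binary result.

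**Number of regions.** Subjects give two scores a day ("one daily score for RLP and one daily score for PLP) for each amputated leg in the 7-day diaries"), so a unilateral amputee has one or two qualifying regions. Section 7.5.2.7 adds: "Bilateral amputees may also receive up to 2 SPRINT Systems for their second leg if it meets the same criteria". A bilateral amputee can therefore have up to four.

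**Primary comparison.** The null hypothesis in 9.1 is "proportion of successes of Group #1 = proportion of successes of Group #2". Section 9.1.2 names the test behind the sample size: "A power analysis of the 2-tailed, 2-sample Mann-Whitney test was conducted with data from the previous feasibility study". Neither mentions a stratum or covariate.

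**Covariates.** Section 9.1.1 names seven baseline variables: "sex, age, baseline pain intensity, time elapsed from amputation, medications affecting pain used at baseline, prosthesis fit, baseline BDI-II score". To these it adds change in pain-medication use. They "will be examined via a covariate analysis to determine their influence on the primary outcome"; nothing visible says that they adjust the primary test. Neither the number of qualifying regions nor bilateral status is listed.

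**Not visible.** Section 7.5.2.1 gives block randomisation and is then redacted. Parts of 9.0 and 9.1 and the text after the power paragraph are also redacted, and no Section 9.1.3 can be seen.

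**The concern.** Unless a subject's regions always respond together, the chance of passing in all of them falls as their number rises. The endpoint's definition therefore creates a strong prognostic factor, and its value is known from the baseline diary. Baseline pain intensity does not stand in for it: a subject with one region at 7 and a subject with two regions at 7 have the same intensity but different chances of success.

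In a trial of 54, the arms can easily differ in the share of multi-region subjects. An unadjusted comparison then carries that difference into the estimated effect, in whichever direction chance put it. If the imbalance is noticed only at the end, any adjustment will have been chosen after the data were seen.

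**Working it through.** **Inputs from the plan.** 27 per group and 1:1 allocation (6.2); two-sided 0.05 (9.1); power above 90% (9.1.2). The success rates behind the power figure are not visible, so that figure cannot be reproduced. A two-proportion calculation without continuity correction gives 90% power at 27 per group for pairs such as 10% v 49%, 20% v 62% or 30% v 73%. The sample size is thus plausible for a difference of about 39-43 points, and it is not in dispute here.

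**Assumptions, not in the plan.** Half of subjects have two or more regions; assignment is simple 1:1; regions within a subject have latent-normal correlation between 0 and 0.8.

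**Step 1: how much harder success becomes.** With independent regions, the chance of passing all k is p^k. For p = 0.65, 0.65² = 0.42 and 0.65⁴ = 0.18. For p = 0.25, 0.25² = 0.06 and 0.25⁴ = 0.004. Over correlations from 0 to 0.8:

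| Per-region success | Two regions | Four regions |
|---|---|---|
| 65% | 42-56% | 18-47% |
| 25% | 6-17% | 0.4-12% |

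**Step 2: how often the arms differ.** The SD of the between-arm difference in the multi-region share is √(2 × 0.5 × 0.5 / 27) = 0.136, about 14 points. A gap of 20 points is 0.20 × 27 = 5.4, so 6 or more subjects. The difference between two Binomial(27, 0.5) counts is 6 or more in absolute value with probability 0.134, or 0.067 in each direction. Given that it is at least 6 in one direction, its mean is 7.13.

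**Step 3: shift under the null.** The expected shift is (imbalance / 27) × (success with one region − success with two or more), and 7.13 / 27 = 0.264.

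| Success, one v two or more regions | Shift |
|---|---|
| 25% v 8% | 0.264 × 17 = 4.5 points |
| 40% v 20% | 0.264 × 20 = 5.3 points |
| 50% v 25% | 0.264 × 25 = 6.6 points |

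**Step 4: error rates under the null** (simulation, 400,000 trials per scenario, same three pairs of rates).
- Over all trials, the mean difference is zero. Two-sided error is 4.8-5.7% unadjusted and 4.9% with Cochran-Mantel-Haenszel (CMH). The small excess comes from the discreteness of the uncorrected test, not from imbalance.
- With imbalance of 6 or more favouring Group #1, one-sided error is about 6-7% unadjusted and 2.2-2.6% with CMH.
- With the mirror imbalance, unadjusted one-sided error falls to 1% or less (0.6-0.8% in most runs), against a nominal 2.5%.
- With imbalance in either direction, two-sided error is about 7.0-7.4% unadjusted.

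**Step 5: power** (per-region success 65% v 25%). When 6 or more extra multi-region subjects fall in Group #1, power is about 74% unadjusted against 85% with CMH at correlation 0. At correlation about 0.5 it is about 77-78% against 84%. Averaged over all randomisations, CMH gains about 0.4 to 0.9 points in these two scenarios. Across other assumed rates the change was mostly under 1 point: one run showed a gain of 4 points and one a loss of 0.1.

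**The case against.** **The comparison is valid as it stands.** A reader might infer that the primary result is biased or its type I error inflated. Neither follows. Randomisation makes the unadjusted difference unbiased, and Step 4 shows a mean of zero and overall error near 5%. The distortion is conditional on a particular imbalance and symmetric: it lowers false positives as often as it raises them. This stands and limits the point to protection of the single trial run.

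**The plan may already deal with it.** A reader might also infer that the trial ignores the region count altogether. The documents do not show that. Stratified blocks or further test detail could sit in the redacted text, and stratified randomisation would shrink the imbalance in Step 2. The point therefore concerns the visible text only. The covariate list in 9.1.1 is visible and explicit, and the count is not in it.

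**The size depends on assumption.** A 50% share makes imbalance most frequent. At a 20% or 80% share, a gap of 20 points occurs in about 6% of trials. The four-region figures need bilateral amputees with all four regions qualifying; the plan gives no frequency for these, and two strata would not separate them. All of this stands.

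**The stratum is imperfect.** Success counts only regions in treated legs, and a second leg may or may not be treated. A diary count would put a bilateral subject with one qualifying region per leg and one treated leg in the upper stratum, although only one region has to respond. This is true, but a variable fixed before randomisation cannot be affected by assignment, so misclassification costs some efficiency and not validity.

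**Regions are analysed elsewhere.** Sections 4.5 and 9.4 examine RLP and PLP separately. Those analyses are exploratory and do not bear on the primary test.

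**Conclusion.** The point holds as a precision and robustness issue. By the plan's own rule the baseline number of qualifying regions is prognostic, yet it is missing from the visible primary comparison and from the 9.1.1 list.

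With half the subjects multi-region and simple 1:1 assignment, about 13% of trials would have an imbalance of 6 or more subjects. In those trials the null difference moves by about 4.5 to 6.6 points, one-sided error becomes about 6-7% or 1% or less depending on direction, and power is about 6-11 points below that of the stratified test when the imbalance goes against Group #1. On average over randomisations almost nothing changes: bias is zero, error is near nominal, and the power gain is mostly under 1 point. The case for acting rests on the low cost and on having the adjustment fixed in advance. It does not rest on any invalidity of the unadjusted test. The figures depend on the assumed share, success rates and correlation, none of which the visible text gives.

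**What to change.** In 9.1, specify the primary comparison as a CMH test stratified by the number of baseline-diary qualifying regions (1 v 2 or more). Count the regions before randomisation and regardless of which leg is later treated. The timing matters because 9.1 itself gives the example of leads placed in a second leg during the home trial. Report the stratified risk difference with its 95% CI, and keep the unadjusted test as a sensitivity analysis.

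Tabulate the count by arm with the baseline characteristics and add it to the 9.1.1 list. Adding it to 9.1.1 alone would not be enough, since that analysis is not stated to adjust the primary test. If the redacted text already stratifies the randomisation by this or a similar factor, the primary analysis should use the same stratum.

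The cost is SAP wording; the diary already holds the data. The one downside is some loss of efficiency from bilateral subjects whose diary count exceeds the number of regions that must respond.

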**7.5.3 Visit 3 - Telephone Follow-up**

All subjects will receive a Telephone Follow-up 24 - 48 hours after each Visit 2 (Lead Placement) to query for any adverse event (AE). All AEs will be followed until resolution. Subjects who return for Visit 2 but are not eligible to be randomized will not receive a follow-up phone call to assess adverse events following lead placement because they will not have participated in the lead placement procedure.

**7.5.4 Visit 4** [REDACTED]

Subjects will return approximately 1 week after the final Visit 2.

[REDACTED]

[REDACTED]

[REDACTED]

**7.5.5 Visit 5** [REDACTED]

The subject will return approximately 2 weeks after the initial lead placement. [REDACTED]

[REDACTED]

**Visit 6** [REDACTED]

The subject will return approximately 3 weeks after the initial lead placement [REDACTED]

[REDACTED]

**Visit 7** [REDACTED]

The subject will return approximately 4 weeks after the initial lead placement. This visit is identical to Visit 4, [REDACTED]

[REDACTED]

For Group #2 subjects who received replacement leads at this visit, there are three options:

1. Proceed to home trial:

If the subject responds to stimulation [REDACTED]  
the subject will be prepared to proceed to the home trial. [REDACTED]

2. Return for another Visit 2:

[REDACTED]

If there is not sufficient time to complete lead placement or the testing, or if the subject does not respond to stimulation, the investigator may present the subject with the option to return for a repeat lead placement visit.

3. Terminate from the study:

If the subject does not wish to continue with further lead placement, they will be terminated from the study if no adverse events (AE) are noted at the 24-48 hour telephone follow-up. If an AE is noted the subject will be followed until the AE resolves.

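### As worded, the primary 4-week pain score omits recorded days after a lead comes out, so for subjects who lose a lead it measures relief with all leads in place

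*Combined protocol and SAP*

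**What the plan says.** Section 9.1 compares the 7-day baseline diary mean with the mean over the first 4 weeks of the home trial, described as "the average of all diary scores during this period". The next sentence narrows this: "For each leg with leads, the average pain scores will only include the days when all leads are in place". One example follows: "if leads are placed in second leg during week 2 of home trial, then only the data from weeks 2-4 will be used". Success requires at least a 50% reduction in every qualifying region. The conclusion is about the whole period: the success rate on treatment is to be greater "than the proportion of successes of the control during the first 4 weeks of the home trial".

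The plan foresees lead problems after placement. Section 7.5.23 allows for unscheduled visits by subjects who "require a bandage change or lead replacement". The Visit 7 entry, at about week 4, sets out options "For Group #2 subjects who received replacement leads at this visit". Section 7.7 provides compensation for lead replacement in Group #2 after Visit 4, which falls at about week 1.

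Section 9.1.5 fills days with no diary score and no obtainable recall with the baseline-week mean. Section 9.5 defines ITT as randomized and implanted subjects analyzed in their randomized group, and its visible text gives no separate day rule. Section 9.3 applies the primary method to the 8-week durability endpoint but repeats only the wording about averaging all scores.

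**The concern.** For late placement the restriction is sensible: a leg should not be scored before its system is in. The sentence is not limited to that case, however. A pain score recorded after a lead has come out is not missing, so section 9.1.5 does not touch it, and section 9.1 removes it. Days are then selected by device status after randomization, and for an active device the removed days are likely to be the worse ones. The visible text sets no minimum number of counted days for a success. The per-protocol limit of 50% concerns missing scores, not excluded days.

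Two matters follow. First, an endpoint read as 4-week success would, for some subjects, be success while all leads are in. Second, two programmers could score the same diary differently, and with 27 subjects per group one reclassification moves a success rate by 1/27 = 3.7 points.

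There is also a narrower overlap. A day with a lead out, no entry and no recall is excluded under section 9.1 but set to baseline under section 9.1.5, and no visible text says which rule prevails.

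**Working it through.** **Figures in the plan.** No stated figure is contradicted. The power statement in section 9.1.2 (over 90% at 5%) cannot be reproduced because the success rates behind it are not visible, and it does not bear on this point. The inputs from the plan are the 28-day window, the 50% bar and 27 subjects per group (section 6.2). Every relief and lead-loss rate below is an assumption.

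**One subject, recorded lead-out days.** With d lead-out days, the all-day reduction is [r_on × (28 − d) + r_off × d] / 28. Under the rule as worded the score is r_on, whatever d is.

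- r_on 60%, r_off 20%: d = 7 gives (12.6 + 1.4)/28 = 50.0%, still a success. d = 8 gives (12.0 + 1.6)/28 = 48.6%, a failure. d = 14 gives 40%.
- r_on 70%, r_off 20%: status first changes at d = 12, (11.2 + 2.4)/28 = 48.6%.

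**One subject, unrecorded and unrecalled lead-out days.** Exclusion gives r_on. Baseline imputation gives r_on × (28 − d)/28.

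- 60% relief: the two readings first disagree at d = 5 (49.3%). At d = 7 they give 60% and 45%.
- 70% relief: d = 9 (47.5%).
- 80% relief: d = 11 (48.6%).

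**Group model.** Each subject's reduction is Normal with SD 30 points, and group means are set so that success with leads in place is 60% v 20%. A lead is lost after 1 to 27 days (uniform). The gap is 1-7 days (uniform), exactly 7 days, or lasts to day 28, and all gaps are capped at day 28. In the main version, pain after loss goes to the sham level, in keeping with the plan's premise: "Both groups are expected to experience a similar placebo effect from the study procedures and use of the devices". The results come from simulation with 2,000,000 subjects per scenario; direct evaluation of the same model agrees within about 0.1 point.

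Group #1 all-day success (60% under the rule) when 10 / 20 / 30% of Group #1 lose a lead:

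| After loss | Gap 1-7 days | Gap 7 days | No replacement |
|---|---|---|---|
| Pain at sham level | 59.4 / 58.8 / 58.3 | 59.0 / 58.1 / 57.1 | 57.9 / 55.7 / 53.6 |
| Pain at baseline | 59.0 / 57.8 / 56.8 | 58.1 / 56.1 / 54.3 | 55.9 / 51.6 / 47.5 |

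At sham level the overstatement is 0.6 to 2.9 points with replacement (0.2 to 0.8 of a subject in 27) and 2.1 to 6.4 points without (0.6 to 1.7 subjects). If half the effect persists and there is no replacement, Group #1 is at 59.0 / 57.8 / 56.8%.

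**Group difference when both groups lose leads and pain returns to baseline.** Group #2 falls from 20% to 19.4 / 18.8 / 18.1% (gaps 1-7 days) or 18.4 / 16.9 / 15.3% (no replacement). The 40-point difference becomes:

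- gaps of 1-7 days in both groups: 39.6 / 39.0 / 38.7;
- no replacement in either group: 37.5 / 34.7 / 32.2;
- 7-day gaps in Group #1 and no replacement in Group #2: 39.7 / 39.2 / 39.0.

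**No true effect.** With 40% success in both groups and pain at sham level after loss, all-day success stays at 40.0-40.1%, so nothing shifts.

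**The case against.** The strongest defence is intent. The sentence opens with legs that have leads, and its example is staged placement, which the plan provides for through repeat Visit 2 sessions and second-leg systems in bilateral amputees. The authors probably had only that in mind. This stands as a reading of intent, but the example is given as an example and the rule is general, so it does not settle how the diary is scored.

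Redaction also counts. The rest of section 7.5.23, all of section 7.6, the text between sections 9.1.2 and 9.1.4, most of section 9.1.4, the end of section 9.1.5 and parts of section 9.5 cannot be seen, and any of them may deal with lead loss. This limits the claim to the visible text.

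The larger figures need long gaps. Visits 4 to 7 are about a week apart (for Visit 5: "The subject will return approximately 2 weeks after the initial lead placement"), and replacement is foreseen, so 8 or more lead-out days, or no replacement at all, should be less usual. That stands, and it also makes unrecorded, unrecalled days uncommon.

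Finally, pain while treated is a defensible target for a pilot study. That is true, but it should be declared and set beside the 4-week result.

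A reader might go further and infer that the ITT result as a whole is an on-lead result, that subjects leave the ITT set, that the rule favours Group #1 in the comparison, or that it inflates false positives. The documents support none of these. Scores are identical for subjects whose leads stay in, ITT membership does not change, the rule applies to both groups with unknown loss rates, and the no-effect model shows no shift.

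**Conclusion.** The concern holds in a limited form, as a minor point. Read literally, section 9.1 drops recorded days after lead loss, and no visible text corrects this. For subjects who lose a lead, the score is then relief with all leads in place, not 4-week relief.

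The size and direction in this trial are unknown. If the device works and pain goes to sham level after loss, Group #1's rate is overstated by about 0.6-3 points when leads are replaced, which is under one subject in 27, and by up to about 6 points with 30% loss and no replacement. The harshest variant, with pain back at baseline and no replacement, reaches 60 − 47.5 = 12.5 points for Group #1. When both groups lose leads, the difference can move by as little as 0.3 points. These figures rest on assumed success rates, spread, loss rates and gap lengths.

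The precedence between sections 9.1 and 9.1.5 and the day rule for the 8-week endpoint are secondary clarifications.

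**What to change.** In section 9.1, for the ITT primary analysis:

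1. Limit the exclusion to days before a leg's lead placement is first complete. From then to the end of week 4, count every recorded or recalled day, whatever the lead status.
2. State that section 9.1.5 governs unrecorded, unrecalled days in that window.
3. Report the mean over days with all leads in place as a per-protocol or sensitivity analysis, with the number of lead-out days by group.
4. In section 9.3, state that the same day-inclusion rule applies to the 8-week endpoint, without carrying the week 1-4 imputation beyond week 4.

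If the sponsor prefers the on-lead score as primary, say so plainly and report the all-days ITT result beside it. If redacted text already settles these points, a cross-reference in section 9.1 is enough.

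The cost is a few sentences and one additional run on diary data already collected. No visit or procedure changes. The downside for the sponsor is that Group #1's success rate may come out slightly less favourable.
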